### 2.5.6 Qualitative Interviews

Qualitative interviews may occur at day discharge (+/- 7 days), Day +30 (+/- 14 days), Day +60 (+/-14 days), Day +90 (+/- 14 days), and/or Day +120 (+/-30 days). Qualitative interviews will occur based on study team and participant choice and may include all, some, or none of the interviews for a participant.

Not obtaining qualitative interviews will not be considered a deviation. Study subjects may be asked to participate in a 20 min interview, permission will be asked to audio-record the qualitative interviews. These may be conducted in person, through video conferencing platforms (such as Zoom), or by phone. Participants will opt-in or out of being audio recorded on the informed consent document.

### **3.0 STUDY ENDPOINTS**

#### **3.1 Primary Endpoint**

The primary endpoint is caregiver HRQOL, as assessed by the PROMIS Global Health scale, at day 120 post-HCT. To be evaluable for caregiver HRQOL, the caregiver must complete this scale at day 120 post-HCT. Caregivers of patients who relapse or die before this endpoint will not be evaluable for this endpoint; both caregiver and patient will be censored on the date the patient was last examined. See **Appendix D** for a copy of all PROMIS PROs.

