#### **4.8 Post-Intervention Evaluation**

PROMIS Patient-Reported Outcomes (PROs) Well-being or HRQOL assessments will be obtained at days 30 (+/- 14) and 120 (+/- 30) post-HCT, during and at the end of the intervention period, respectively. The surveys will be obtained through Qualtrics, which will be linked directly to the Roadmap 2.0 app on the mobile phone. Based on prior work, our Study Team has experience administering PROMIS PROs on mobile devices. If a participant relapses, our team will continue to collect clinical data post-transplant. In the event of a relapse, the patient will be censored, and we will not collect any further surveys from the patient or caregiver.

Missing surveys will not be considered a protocol deviation.

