#### **4.9 Participant Withdrawal**

At any time, a participant may request that her or his data no longer be collected, that her/his data be removed from the study database, that their physiologic data no longer be collected or used for research now or in the future. The participant may make this request to the Research Coordinator or to any member of the Study Team or the BMT clinical team. The participant's research information will be deleted from the study database (with a comment that the participant withdrew consent for collection). Upon withdrawal, the participant may keep all physiological monitoring devices used in the study. A note will be made in the study record documenting the reason the patient withdrew from the study.

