## **5.11 Analysis of Primary Endpoint**

Analysis will be an intent-to-treat analysis that includes all caregivers. Mean Global Health scores for each arm at day 120 will be compared using a two-sample *t*-test (or Wilcoxon Rank Sum test if non-normality is apparent) with a significance level of 0.05. Linear regression models will be performed to complement the results of the *t*-test and adjust for specific baseline caregiver characteristics (e.g., demographic, social, environmental) to increase the precision of our inference. We plan to do analyses separately for allo dyads, auto dyads, and pediatric dyads, although we have only powered the study for the analysis in the allo dyads. There is a possibility that patient characteristics will be unbalanced since our randomization scheme will be applied to caregivers. Thus, our models also will assess potential moderating or mediating effects, described below.

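### The primary analysis is called intent-to-treat in all caregivers, but caregivers of patients who relapse or die are non-evaluable and caregiver surveys stop at relapse

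*Combined protocol and SAP*

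**What the plan says.** Section 3.1 defines the outcome: "The primary endpoint is caregiver HRQOL, as assessed by the PROMIS Global Health scale, at day 120 post-HCT". It then restricts who counts. Completion is required ("To be evaluable for caregiver HRQOL, the caregiver must complete this scale at day 120 post-HCT"), and two patient events remove the caregiver: "Caregivers of patients who relapse or die before this endpoint will not be evaluable for this endpoint". For those dyads, "both caregiver and patient will be censored on the date the patient was last examined".

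Section 4.8 adds a data-collection rule for one of the two events: "In the event of a relapse, the patient will be censored, and we will not collect any further surveys from the patient or caregiver". Clinical data continue to be collected after relapse. No section states that surveys stop when the patient dies.

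The analysis sections describe a wider population. Section 5.11 says: "Analysis will be an intent-to-treat analysis that includes all caregivers". Section 5.10.1 places in the primary population everyone who enrolled, consented and completed the baseline measures. The test in 5.11 is a two-sample t-test on day-120 means, or a Wilcoxon test if the data look non-normal. The primary objective in 2.3.1 is not limited to caregivers of relapse-free survivors.

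Section 5.7 allows for three losses: 5% not transplanted, 8% deaths before day 120 and 10% without a day-120 questionnaire. It has no term for relapse.

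**The concern.** The analysis sections promise a comparison of everyone randomized who has a baseline. The endpoint and follow-up sections deliver a comparison of caregivers whose patient stayed alive and relapse-free and who returned the day-120 form. Membership of that second group is settled after randomization, so randomization no longer guarantees that the arms are comparable. The design rationale in 2.1 and 5.1 rests on exactly that guarantee.

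The protocol does not treat patient outcome as plainly independent of arm. Section 1.5 suggests that caregiver well-being may improve patient outcomes, and 5.13.3 compares survival between arms.

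Two features make this more than a labelling problem. Censoring is a time-to-event device and has no function in a comparison of day-120 means, so 3.1 does not tell the analyst what to do with these caregivers. And most analysis choices can still be settled before database lock, whereas a survey that was never sent cannot be analysed later. The caregiver of a relapsed patient can still answer the scale; only the protocol prevents it.

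**Working it through.** **Step 1. Can the rules be reconciled?**

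| Event | Section 3.1 | Section 4.8 | Sections 5.10.1 and 5.11 |
|---|---|---|---|
| Patient relapses | Caregiver non-evaluable, censored | Caregiver surveys stop | Caregiver included |
| Patient dies | Caregiver non-evaluable, censored | No survey stop stated | Caregiver included |
| No day-120 form | Caregiver non-evaluable | Not a deviation | Included if baseline done |

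The primary test uses observed day-120 scores only. No section gives an imputation rule, a composite outcome or a sensitivity analysis for the excluded caregivers. The contradiction stands.

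**Step 2. Reproduce the plan's sample size (5.7; powered for adult allogeneic dyads only).** Inputs: difference 5 points, SD 10, two-sided alpha 0.05, power 0.80.

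- t-test: 63.8 per arm. Dividing by the Wilcoxon efficiency 3/π = 0.955 gives 66.8, so 67, which is the plan's figure.
- Losses added: 5% + 8% + 10% = 23%. 67 × 1.23 = 82.4, so 83, also the plan's figure.

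**Step 3. Day-120 scores expected from 83 per arm, before relapse.**

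- Losses added: 83 × 0.77 = 63.9; t-test power 0.80.
- Losses multiplied: 83 × 0.95 × 0.92 × 0.90 = 83 × 0.7866 = 65.3; t-test power 0.81.

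So 21% to 23% of the all-caregiver population is outside the test before anyone is excluded for relapse.

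**Step 4. Add relapse.** The documents give no rate. I assume 5%, 10% and 20%, multiplied onto the 65.3.

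| Assumed relapse | Evaluable per arm | t-test power | Wilcoxon power | Accrual per arm for 67 evaluable |
|---|---|---|---|---|
| 5% | 65.3 × 0.95 = 62.0 | 0.79 | 0.77 | 90 |
| 10% | 65.3 × 0.90 = 58.8 | 0.77 | 0.75 | 95 |
| 20% | 65.3 × 0.80 = 52.2 | 0.72 | 0.70 | 107 |

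**Step 5. Can the bias be signed?** All inputs here are assumptions, chosen to test the direction only.

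*Different effect in the excluded.* Take a 5-point benefit in those kept and 15% excluded in both arms.

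- Benefit 0 in the excluded: 0.85 × 5 + 0.15 × 0 = 4.25. The evaluable-only result is higher than the all-caregiver effect.
- Benefit 7 in the excluded: 0.85 × 5 + 0.15 × 7 = 5.3. It is lower.

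*Different exclusion rates.* Take means of 50 and 55 in those kept, and excluded caregivers 10 points lower in each arm. The evaluable-only difference is always 5.0.

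- Control 20%, intervention 10%: control 0.8 × 50 + 0.2 × 40 = 48; intervention 0.9 × 55 + 0.1 × 45 = 54; all-caregiver difference 6.0.
- Both 15%: 53.5 − 48.5 = 5.0.
- Control 10%, intervention 20%: 53 − 49 = 4.0.

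The gap can be positive, negative or zero.

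**The case against.** Several points on the other side have force.

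- **Death is treated differently from relapse.** A reader might infer that surveys stop after either event. The documents say so only for relapse. Unrecoverable loss of data is therefore shown only for relapse, the event whose rate is not given.
- **A reader might infer that the plan exaggerates the benefit**, on the view that the excluded caregivers are the most strained and gain least. The documents say neither. The hypothesis concerns caregivers of transplant patients generally, and step 5 shows that the gap can go either way.
- **A large difference in relapse or death between arms is not documented.** Patients in the intervention arm receive only the control version of Roadmap 2.0. With equal exclusion rates and the same effect in kept and excluded caregivers there is no gap.
- **The power loss may be small.** Section 5.7 describes its loss rates as inflated, and at 5% relapse the t-test still has power 0.79.
- **The plan has partial safeguards.** Survival is compared by arm (5.13.3), Global Health is collected at day 30 (3.2.1), and the mixed model in 5.13.2 can use earlier scores from caregivers excluded later.

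These points limit any claim about the size of the problem. They do not remove the contradiction. The mixed model is listed under exploratory endpoints and cannot supply a score that was never requested, and a survival comparison says nothing about the caregiver's quality of life.

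**Conclusion.** The plan is wrong as written. Sections 3.1 and 4.8 cannot both be followed alongside 5.10.1 and 5.11. The comparison that will actually be made is an evaluable-case analysis in a subset defined after randomization, and for relapse the missing scores are lost for good. This conclusion rests on the text alone.

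No size or sign can be given to the bias: it depends on relapse rates, arm differences and the scores of excluded caregivers, none of which the documents supply. The effect on numbers is firmer. About 64 to 65 of 83 per arm are evaluable on the plan's own rates. Under an assumed 5% to 20% relapse this becomes about 62 to 52, with t-test power of about 0.79 to 0.72 for a 5-point difference and an SD of 10.

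**What to change.** 1. **Relapse (3.1, 4.8).** Delete relapse as a reason for non-evaluability. Keep offering the caregiver the day-30 and day-120 app surveys after relapse, with the option to decline, and analyse those scores in the arm randomized.
2. **Death (3.1, 5.11).** Remove the censoring language and state how these caregivers enter the primary comparison. Report deaths by arm. Add a sensitivity analysis over a stated range of scores for bereaved caregivers, varied by arm. As a guide to scale, at the plan's 8% deaths a 10-point shift in one arm's bereaved caregivers moves that arm's mean by 0.08 × 10 = 0.8 points. If these caregivers stay excluded, drop the claim that all caregivers are included and name the restricted population in 5.10.1 and 5.11.
3. **If the relapse exclusion is kept instead.** Drop the intent-to-treat label, name the restricted population, add a relapse term to the losses in 5.7 and restate the power.

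The cost is protocol and consent wording. The surveys already run through the app and the caregiver scale has 10 items, so no visit is added. The downside is some burden on caregivers at a hard time, and possibly more variable scores. In return, under item 1 relapse no longer reduces the evaluable number below about 65 per arm, apart from caregivers who decline. If caregivers of patients who die are also followed, so that only the 5% and 10% losses remain, 83 × 0.95 × 0.90 = 71.0 per arm are evaluable and t-test power is 0.84.

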#### **3.2 Exploratory Endpoints**

- 3.2.1 Caregiver HRQOL will be assessed by the PROMIS Global Health and Profile 29+2 scales at baseline (pre-intervention) and days 30 post-HCT.
- 3.2.2 Caregiver and patient HRQOL will be assessed by the PROMIS Companionship scale at baseline (pre-intervention), and days 30 and 120 post-HCT.
- 3.2.3 Caregiver and patient HRQOL will be assessed by the PROMIS Self-Efficacy for Managing Symptoms and Self-Efficacy for Managing Daily Activities scales at baseline (pre-intervention), and days 30 and 120 post-HCT.
- 3.2.4 Caregiver and patient HRQOL will be assessed by the PROMIS Positive Affect and Well-Being scale at baseline (pre-intervention), and days 30 and 120 post-HCT.
- 3.2.5 Caregiver and patient HRQOL will be assessed by the PROMIS Emotional Support at baseline (pre-intervention), and days 30 and 120 post-HCT.

- 3.2.6 Caregiver and patient HRQOL will be assessed by the Perceived Stress Scale at baseline (pre-intervention), and days 30 and 120 post-HCT.
- 3.2.7 Caregiver and patient HRQOL will be assessed by the Resilience, Optimism and Gratitude scales at baseline (pre-intervention), and days 30 and day 120 post-HCT.
- 3.2.8 Patient HRQOL will be assessed by the PROMIS Sleep Disturbance scale at baseline (pre-intervention), and days 30 and 120 post-HCT.
- 3.2.9 Caregiver and patient negative and positive dyadic interaction will be assessed by measures of the Dyadic Relationship Scale at baseline (pre-intervention), and days 30 and 120 post-HCT.
- 3.2.10 Caregiver HRQOL will be assessed by the TBI-CareQOL (PROMIS affiliate) Caregiver Anxiety at baseline (pre-intervention), and days 30 and 120 post-HCT.
- 3.2.11 Caregiver HRQOL will be assessed by the TBI-CareQOL (PROMIS affiliate) Caregiver Strain scale.
- 3.2.12 Activity data. Caregiver and patient activity (steps) and sleep will be measured continuously from the start to the end of the intervention (day 120 post-HCT) through wearable sensors.
- 3.2.13 Health care utilization data. Patient health care utilization data (e.g., total count of hospital days, emergency department visits, readmissions, and ambulatory care clinic visits) will be captured through the electronic health record as well as self-report (i.e., if the patient is re-admitted at an outside hospital other than a participating site). Caregiver health care utilization data (e.g., hospital admissions, emergency department visits, and ambulatory care clinic visits) will be collected through self-report at the day 30 (+/-14) and day 120 (+/- 30) post-HCT PRO assessment period. The study team may access the electronic medical records for 1 year from the date of study enrollment.
- 3.2.14 Mobile Application Rating Scale (MARS) was added to the day 120 questionnaire to obtain user experience of the Roadmap 2.0 app.
- 3.2.15 Social Rhythms Application. We are interested in looking at how circadian rhythm may affect the participant's overall health. Participants may upload retroactive data from the Fitbit and will receive a personalized report about their circadian rhythm. Participant will be encouraged to upload their data at baseline (+/- 14 days), day 30 (+/- 14 days), and day 120 (+/- 30 days).

## **4.0 PATIENT ENROLLMENT AND EVALUATION**

### **4.1 Participant Recruitment**

The Adult and Pediatric BMT Programs at the participating sites have regularly scheduled New Patient Evaluation meetings where patients being considered for BMT are presented and discussed. Investigators and study coordinators attend the meetings and will identify potential study subjects who meet eligibility for the non-invasive, wearable activity monitoring device. Study team members will recruit subjects to the study around the time of patient admission to undergo allogeneic or autologous BMT in the inpatient Adult or Pediatric BMT Units. Permission to approach will be obtained from subjects' primary BMT physician prior to attempting to recruit them to the study.

### **4.2 Participant Enrollment and Evaluation**

Participants (caregiver-patient dyads) will be approached for this study after the decision to proceed with transplantation is made by the patient. Caregivers will be identified by the patient as the primary caregiver providing at least 50% of the caregiving needs. Multiple caregivers are not allowed by study design. Eligibility criteria will be verified by the Study Team. Ineligible participants will proceed off study and no further follow-up will be obtained.

### **4.3 Informed Consent Process**

Patient and Caregivers will be told about the study in detail, and will be given a copy of the consent to look through. If the patients and caregivers decide that they want to move forward with participation, the caregiver (who will always be an adult) will be provided with an access code and instructions on how to download the Roadmap 2.0 application on their phone or tablet (iPhone or Android). The application cannot be used without an access code. Once the access code is entered and confirmed, the caregiver will be presented with an electronic copy of the consent on the phone, and will have to click the button to confirm their willingness to proceed. After the caregiver has completed the consent on their phone or tablet, they will be provided with another access code for the patient, who might be an adult or a minor. The patient will then use this access code to open the app on their own device and go through their own electronic consent/assent process. Once the patient has completed the consent/assent, the pair will be officially enrolled in the trial. The database will store the access codes and the timestamps of when the electronic form was completed. The link between the access codes and the patient identifiers will be stored by the study team in a separate location from the application server so that the identity of the participants will never be stored within the application or the supporting application server, thus protecting privacy.

The consent process relies on a waiver of documentation, meaning that

participants will not use their actual signature to denote consent since the act of consenting is done by checking boxes within the app. The app will know which site's consent/assent to present to a subject based on the center ID, study ID, and access code.

#### **4.4 Transplant Protocol Registration**

Before randomization occurs, the Research Coordinator must state through the OnCore Clinical Trials Management System the baseline caregiver biological characteristics (e.g., age, gender, race/ethnicity). This will avoid potential biases that preferential use of gender, for example, on one arm could confer to the study. At this stage, the Research Coordinator will also verify that the patient is still a candidate for transplantation, and both caregiver and patient are eligible for this clinical trial.

#### **4.5 Randomization**

Once the caregiver-patient dyad is deemed eligible and has provided written informed consent, the Research Coordinator will confirm eligibility. The study statistician, [name] (Co-I), will create a randomization list before the study begins enrollment using the statistical package R. [name] will then forward the list to the Data Manager/Research Coordinator, who will be responsible for enrolling patients and assigning them to the correct study arm. Caregiver-patient dyads will not be randomized more than 21 days from the planned initiation of conditioning. All patient treatments related to the transplant should be scheduled PRIOR to randomization. This includes planning an admission date and ensuring that donors can be used in a coordinated fashion with the planned transplant.

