### **5.4 Randomization**

Blocked randomization will be used to limit bias and achieve an equal distribution of participants to the treatment and control arms. This approach will recruit participants in small blocks to ensure that half of the participants within each block will be allocated to the treatment and the other half to the control. The size of the blocks will be permuted to limit selection bias, and within each block, the

order of patients will be random. Randomization will be stratified by type of transplant (adult allo, adult auto, pediatric), so that three separate randomization lists will be created. The study statistician, [name] (Co-I), will create the randomization lists before the study begins enrollment using the statistical package R. Assignments will be allocated in list order, and an assignment will not be reused with future patients if a patient later declines to participate after being randomized. Adequate training will be given to the Project Manager and Research Coordinator, including enrollment of participants, allocation of treatment arm, and training the participants.

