## **5.10 Analysis Populations and General Analysis Guidelines**

### **5.10.1 Primary Analysis Population**

All participants enrolled, consented, and completing at least the baseline outcome measures will be included in the primary analysis population. Analyses for the primary and secondary endpoints will use the primary analysis population: Caregivers of adult patients [age  $\geq 18$  years] will be analyzed separately from caregivers of pediatric patients [age 5-17 years]). The primary analysis will occur once all patients have been followed for 120-days post-transplant, data adjudication completed, and data are locked.

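### The complete randomization list goes to the staff who enrol dyads and assign arms, so allocation is not concealed from them as written

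*Combined protocol and SAP*

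**What the plan says.** Section 4.5 states that the study statistician "will create a randomization list before the study begins enrollment using the statistical package R" and will then "forward the list to the Data Manager/Research Coordinator, who will be responsible for enrolling patients and assigning them to the correct study arm". In the same section, once a dyad has consented, "the Research Coordinator will confirm eligibility". Section 5.4 has three lists (adult allogeneic, adult autologous, pediatric) with 1:1 blocks. It trains the Project Manager and Research Coordinator in duties "including enrollment of participants, allocation of treatment arm, and training the participants".

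The stated safeguards are these:
- Section 5.4: "The size of the blocks will be permuted to limit selection bias". No sizes are given.
- Section 5.4: "Assignments will be allocated in list order, and an assignment will not be reused with future patients if a patient later declines".
- Section 4.4: "Before randomization occurs, the Research Coordinator must state through the OnCore Clinical Trials Management System the baseline caregiver biological characteristics". The coordinator also re-verifies eligibility at this stage.
- Section 4.5: dyads are randomized no more than 21 days before planned conditioning, with transplant treatment already scheduled.

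Section 5.5 leaves investigators, participants, statistician and outcome staff unblinded. Section 5.6 makes the primary endpoint caregiver self-report. Section 5.11 compares day 120 means by a two-sample t-test or rank-sum test, with regression as a complement.

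On baseline data, Section 4.7 asks for the patient-reported outcome (PRO) surveys before the intervention and does not mention randomization. Section 5.10.1 then says that those "completing at least the baseline outcome measures will be included in the primary analysis population".

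**The concern.** Concealment means that whoever decides whether and when a dyad enters cannot know the arm it will receive. Here the list, the enrolling and the assigning are given to the same role. A list holder can, without intending to, randomize one waiting dyad before another or encourage one more strongly, according to the next arm.

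Other protections are thin. Nobody is blinded, the caregiver rates their own outcome, and the primary test makes no adjustment for baseline differences. Sections 2.1 and 5.1 rest the design on known and unknown factors being balanced except by chance. That no longer follows if entry can respond to the coming assignment, and adjustment for measured characteristics cannot repair imbalance in unmeasured ones.

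The baseline rule is a different problem. If a caregiver can learn the arm before answering, then whether and how they answer may depend on the arm, and answering decides who is analysed.

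**Working it through.** **1. Do the safeguards hide the next arm?**

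| Safeguard | What it does | Hides the next arm from a list holder? |
|---|---|---|
| Varying block sizes (5.4) | Hinders guessing from past assignments | No |
| List order, no reuse (5.4) | Stops skipping or recycling an assignment | No |
| OnCore registration, eligibility check (4.4) | Records characteristics before randomization | No |
| 21-day limit, scheduled transplant (4.5) | Narrows the room for timing | No |
| Separate outcome collectors (5.5) | Acts after assignment | No |

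**2. What varying block sizes can achieve.** As an illustration, suppose a recruiter without the list always guesses the arm that has had fewer assignments so far, tossing a coin when tied. In simulation with assumed block-size mixes from {2, 4} to {4, 6, 8}, the guess is right about 72% to 68% of the time. A list holder is right 100% of the time, whatever the block sizes.

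**3. The plan's sample size.** Section 5.7 gives 67 caregivers per arm for power 0.80, two-sided 0.05, difference 0.5 SD, SD 10. An exact t-test calculation needs 64 per arm. Dividing by the rank-sum efficiency of 0.955 gives 64 / 0.955 = 67.0, and a simulated rank-sum test at 67 per arm has power 0.796. So 67 reproduces for the rank-sum test; t-test power at 67 is 0.819. The concealment point does not depend on this figure, which is used only for the standard error.

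**4. What a selection bias would do.** The standard error of the difference is 10 × √(2/67) = 1.73 points. With a bias of b points and no true effect, type I error = 1 − Φ(1.96 − b/SE) + Φ(−1.96 − b/SE).

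| Assumed b (points) | b/SE | Two-sided type I error |
|---|---|---|
| 0 | 0 | 0.050 |
| 0.5 | 0.29 | 0.060 |
| 1 | 0.58 | 0.089 |
| 2 | 1.16 | 0.212 |

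One way to picture b: if a share f of intervention enrolments is steered toward caregivers who would score d points higher, then b = f × d. For example 0.10 × 5 = 0.5, 0.20 × 5 = 1 and 0.20 × 10 = 2. The documents support no particular f or d.

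**5. Order of baseline and assignment.** Section 4.4 lists what is recorded before randomization and does not mention the PRO surveys. Section 2.5.1 schedules training for dyads already randomized. The Time and Events Table puts questionnaires and arm-specific training in one pre-admission column and has no row for randomization. Nothing requires baseline before assignment. Section 5.11 describes an intent-to-treat analysis of all caregivers, whereas Section 5.10.1 restricts the population to baseline completers. Both cannot hold for a randomized caregiver without a baseline survey.

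**The case against.** Several points on the other side are fair.

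- The slash in the Section 4.5 job title could mean two people. Even so, the sentence gives the list to whoever enrols and assigns.
- A reader might infer that one person approaches, consents, enrols and trains every dyad with the list in hand. The documents do not go that far. Section 4.1 has study team members recruit with the transplant physician's permission, and under Section 4.3 consent is completed in the app with timestamps. Enrolling, checking eligibility, assigning and training are what the text supports.
- The trial has several sites (Sections 4.10, 4.13, 4.16) but only three lists, stratified by transplant type and used in order. Separate sites could hardly work down a shared list independently, so some common point of assignment is implied. It is therefore not established that recruiters at every site see the list. This is an inference, and no such step is written down.
- Registration before randomization, the 21-day limit, list order and no reuse restrict manipulation and leave a partial audit trail. They do not conceal.
- A reader might take the loose baseline timing as a further reason why allocation is unconcealed. It has no bearing on concealment. Nor do the documents direct that baseline follow assignment: the app is installed at consent and carries the survey, so doing baseline first is feasible. The text is silent on the order.

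**Conclusion.** As written, allocation is not concealed from enrolling staff, and varying the block sizes does not remedy that. This rests on the wording of Sections 4.5 and 5.4 and on the absence of any described concealed release; it needs no assumption about anyone's conduct. It should be corrected, because selection bias cannot be reliably removed in the analysis.

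The size is unknown. The type I error figures of about 0.06, 0.09 and 0.21 hold only for assumed biases of 0.5, 1 and 2 points, with SD 10, 67 per arm and an unadjusted comparison. A reader might infer that a stated fraction of the 5-point target effect (0.5 × 10) is at risk. The documents give no steering rate or score gap from which such a fraction could be derived.

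The baseline rule is a separate and secondary defect. It permits selection after randomization, and Sections 5.10.1 and 5.11 contradict each other.

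**What to change.** **Concealment (Sections 4.5 and 5.4).** The statistician loads the three stratum lists, or the remaining assignments if enrolment is under way, into a locked central randomization module. REDCap is a natural choice because Section 4.13 already lists it among the study systems. No enrolling staff see the list or the block sizes. One assignment is released at a time, after consent, eligibility and transplant type are recorded and completion of the baseline PRO surveys in Qualtrics is confirmed. If concealed release already happens in practice, the protocol should describe it.

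**Baseline and population (Sections 4.7, 5.10.1 and 5.11).** Require baseline before randomization from now on. Define the primary population by randomization, so that Sections 5.10.1 and 5.11 agree. The second step is still needed with the first in place, because dyads already randomized would otherwise remain subject to the completion condition.

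**Cost.** The sample size and the arms do not change. The work is a modest system set-up, a linked or manual check of Qualtrics completion, and rewording. Dyads slow to complete baseline will be randomized later, and those who never complete it will not be randomized, so accrual may suffer somewhat.
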